Institutional Review Board Intervention/Interaction Detailed Protocol

Principal Investigator: [name]

Project Title: Understanding the effects of non-invasive transauricular vagus nerve stimulation (taVNS) on neural networks and autonomic nervous system: a randomized double-blind sham-control mechanistic trial in healthy participants

Version Date: 08/01/2023

Version Name/Number: 2022P0023200

1. Background and Significance

Transauricular vagus nerve stimulation (taVNS) is a newer delivery system, using a non-invasive stimulation device placed at the concha or tragus of the ear, which does not require surgery; therefore it is more accessible and naturally less risky to patients(1). The taVNS field is growing exponentially in the last few years, and has been predominantly focused on clinical trials showing potential therapeutic benefits for various pathologic conditions, such as epilepsy, schizophrenia, migraine, Parkinson's disease, tinnitus, impaired glucose tolerance, and atrial fibrillation(2).

There is much to discuss about taVNS and its effects on biological processes in the central and peripheral systems. To study how taVNS impact physiological activity, ideally, a biological marker could provide information that the auricular nerve was truly stimulated, causing an effect on intracranial structures. However, without a reliable biomarker, we may not thoroughly learn from the taVNS results and may not have the best interpretation of its effects.

Electroencephalography (EEG) has proven to be a useful tool in understanding the mechanisms behind non-invasive brain stimulation and its effect on brain connectivity. EEG measurements are based on electrical potential differences between electrodes on the scalp. A potential difference is caused by the propagation of the current flow induced by synchronized postsynaptic potentials in pyramidal neuron cell membranes. These measurements allow for the evaluation of effective connectivity between different cortical and subcortical regions and provide high temporal and spatial resolution for the analysis of brain stimulation effects, such as those of Transcranial Magnetic Stimulation (TMS) and transcranial direct current stimulation (tDCS)(3, 4).

Based on that, EEG is seen as a promising imaging tool to provide biomarkers for taVNS. It is a reliable, non-invasive, and inexpensive method to measure and quantify cortical activity. Following through this thought process, our team of researchers has performed a systematic review, demonstrating preliminary information that taVNS could influence cortical activity, mainly increasing EEG power spectrum activity in lower frequencies (delta and theta). However, divergent results in higher frequencies (alpha), and in changes on early ERP components related to inhibitory tasks were also detected. A high heterogeneity between the studies was found; therefore future more homogeneous,

bigger, and well-designed studies are needed to make stronger conclusions about the effects of taVNS in brain activity measured by EEG(5).

Alpha asymmetry, which assesses the relative alpha band activity between the brain hemispheres, particularly at frontal electrodes, is a frequently researched EEG biomarker. Previous literature has used this biomarker to analyze the approach-withdraw hypothesis(6, 7), which holds that the right frontal side of the brain is associated with withdrawal behaviors while the left frontal side is associated with approach behaviors. Since alpha is associated with low brain activity, an increase in alpha on the left side of the brain suggests lower activity and may therefore suggest a lack of approach behavior. This concept helps to explain some results in the alpha band at the left side hemisphere in depressed patients(8).

Additionally, EEG electrodes record the activity of neuronal populations(9). Using this data, it is possible to examine the relationships between several brain regions and the brain's network structure and activity. Functional Connectivity (FC) is a general term used to describe connections between brain regions. It can be assessed in a variety of methods, such as utilizing coherence to denote synchronized activity between brain regions(10). Studies have shown that changes in the normality of large-scale brain networks, such as the default mode network (DMN) (11, 12) and affective network (AN)(13), or the dysconnectivity of some brain regions, such as corticolimbic pathways(14), are related with the psychiatric conditions, for example depression. So, FC has proven to be effective to investigate network dysfunction (15). Based on that, quantitative electroencephalography can be used to assess the effects of taVNS on brain activity; however, more studies are needed to systematically establish the specific effects and metrics that would reflect the non-invasive stimulation through the auricular branch of the vagus nerve.

Peripherally, the vagus nerve and sympathetic nervous system mediate the heart's contractile and electrical function(16). This regulation promotes the heart's pacemaker ability and controls it through physiological manifestations of the body, known as sinus depolarizations. Heart rate variability (HRV) records the changes per beat of sinus depolarization, thus, non-invasively describing vagal influences on the sinus node(17). Given this function, HRV has been seen and studied as a prominent biomarker for neurocardiac function, being associated with an individual's well-being and the likelihood of morbidity, mortality, and stress(18, 19).

In the context of taVNS, HRV has been recorded in many trials, and stimulation has been thought to modulate HRV(16, 20, 21). Considering that a decreased HRV has been related to morbidity and mortality of different diseases through mechanisms such as over-activity of the sympathetic nervous system, inflammatory response, and oxidative stress, the vagal nerve modulation of taVNS is thought to directly impact HRV and its sinus regulation(22, 23). In fact, some trials have already conveyed that taVNS can increase HRV in healthy subjects, thus sustaining this hypothesis(20). However, there is still a lack of understanding on whether different taVNS parameters can affect HRV differently. According to some studies(24, 25), taVNS may also influence nociception and pain perception, and that can lead to potential applications to a variety of painful illnesses, including headache, trigeminal allodynia, chronic pelvic pain, and fibromyalgia(26). The overlapping anatomical pathways between the nociceptive system and the central projections of the vagal afferents may be the cause of the potential mechanisms by which VNS modifies pain perception(27).

Regarding the vagal projections, some studies have demonstrated the vagal role in modulating pain pathways(25, 28-36), the inflammatory system and cortisol levels (37-40), and the gut microbiota (41-43). Several markers such as quantitative sensory testing (QST) (44-46), salivary cortisol (37, 47, 48), and salivary microbiota (49) have been used to measure pain and inflammatory systems, and the gut microbiome respectively. Although, there is still a need for more data to understand the mechanisms of taVNS on these systems.

Indeed, taVNS have been shown to be a safe, portable, and feasible tool (50, 51). Our group has demonstrated its safety through a systematic review and meta-analysis on the topic (Safety of transcutaneous auricular vagus nerve stimulation(taVNS): A systematic review and meta-analysis – peer review). Moreover, several studies have shown promising results of taVNS to treat various disorders such as depression, anxiety, Alzheimer's disease, headache, obesity, and diabetes(2, 52-55). However, no mechanistic studies have investigated the taVNS neural network and autonomic nervous system's effects of this technique. Therefore, we aim to assess how taVNS can affect EEG metrics and HRV and assess its safety. Also, we aim to evaluate predictors that can influence the response to taVNS, so understanding the variables associated with response to taVNS can help the design of future clinical trials to maximize the effects of this intervention.

2. Specific Aims and Objectives

Our goal is to perform an exploratory, mechanistic randomized double-blind sham-control trial in healthy participants, to assess the physiologic effects of a single session of bilateral taVNS, on neural networks and autonomic function.

The specific aims of this experiment are as follows:

Aim 1: We aim to compare the neurophysiologic effects of a single session of active taVNS versus sham taVNS in Frontal Alpha Asymmetry, Functional Connectivity and Phase Synchrony of DMN using EEG on a processing emotional facial expressions and a Go/NoGo task. We expect to find differences in face-related frontal alpha asymmetry between active taVNS versus sham taVNS in healthy controls. Also, regarding the DMN, we expect that taVNS decreases FC between DMN and other areas.

Aim 2: As a second aim, we will measure the effects of one active taVNS session versus sham in heart rate variability total power, very low frequencies (VLF), low frequencies (LF), and high frequencies (HF), and LF/HF ratio. We expect the taVNS to increase HF and decrease LF/HF ratio due to parasympathetic activation. Furthermore, the standard deviation of the R-R intervals (SDRR), the count of R-R intervals that differed more than 50 ms (NN50), the percentage of NN50 (pNN50), and the root mean square of the difference between successive R-R intervals (RMSSD) will be measured and we expect an increase on those metrics as well. We will also explore a non-linear method to calculate the short-term detrended fluctuation exponent (DFA-alpha1).

Additionally, we aim to assess the effects of taVNS in healthy subjects after one single session in some exploratory related outcomes.

3. General Description of Study Design

We will perform a randomized double-blind sham-control trial. We will randomize 44 healthy subjects, who will receive one single session of active taVNS or sham taVNS at the Neuromodulation Center/ Cambridge Spaulding Hospital.

Mass General Brigham Institutional Review Board
Intervention/Interaction Detailed Protocol

	Consent and Screening	Baseline	Intervention	Post intervention
	Visit 1 (online)	Visit 2	Visit 2	Visit 2
Demographics	X			
Medical History	X			
Consent form	X			
Beck depression inventory	X			
EHI/SF	X			
Pregnancy test	X			
BMIS		X		X
VAS-F		X	X	X
EEG		X	X	X
HRV		X	X	X
QST		X		X
Side Effects Questionnaire for taVNS				X
Success of blinding questionnaire				X
Active taVNS			X	
Approximate visit time	60 min	60 min	60 min	30 min

Table 1: Visits Schema

4. Subject Selection

In this study, we will randomize 44 healthy subjects, and they will need to meet the following inclusion criteria and none of the following exclusion criteria:

Inclusion Criteria:

1. Able to provide informed consent to participate in the study.
2. Subject is older than 18 years.
3. Subjects should be naive to the stimulation (taVNS)

Exclusion Criteria:

1. Pregnancy.
2. Subjects who have had a neuropsychiatric or a cardiac disorder diagnosis and have received treatment and chronic medication in the past six months, or who have functional deficits as a result.
3. History of alcohol or drug abuse within the past 6 months as self-reported.
4. Presence of the following contraindication to transauricular vagus nerve stimulation
 - a. Ferromagnetic metal in the head and in the cranium (e.g., plates or pins, bullets, shrapnel)
 - b. Implanted cranial electronic medical devices (e.g., cochlear implants)
 - c. Implanted cardiac devices (e.g., pacemaker)
5. Unstable medical conditions (e.g. uncontrolled diabetes, uncompensated cardiac issues, heart failure or chronic obstructive pulmonary disease).
6. Uncontrolled epilepsy, as defined by previous clinical seizure in the past 3 months in patients with treatment for epilepsy.
7. Suffering from severe depression (as defined by a score of >30 in the Beck Depression Inventory).*

*If a subject screens out due to severe depression they will be provided with a local resource list (as recommended by Cheatle, 2014) (56). If the subject is presenting with suicidal ideation, the medical monitor will be contacted to provide further evaluation and instruction. Study participant will be escorted to the emergency room for assessment and triage if: spontaneous expression of suicidal ideation and/or BDI question 9 answers of 2 or 3.

The safety of taVNS in the pregnant population (and children) has not been assessed and therefore pregnant women (and children) will be excluded. Women of child-bearing potential will be required to take a urine pregnancy test during the screening process.

Potential subjects will be identified by the following sources:

1. Flyers posted in public areas across the Boston-land region.
2. Internet and newspaper advertisements.
3. Advertisements posted in public transportation (The T)
4. Via the Rally platform by Mass General Brigham Research.
5. Potential subjects might also be identified through their medical records (epic LMR, etc.)
6. Via the Partners Healthcare Research Patient Data Registry (RPDR) and Patient Gateway (Research Invitations allow for direct communication with any eligible subjects who have not opted out of receiving Research Invitations.)

Eligible subjects will contact, or give permission to be contacted, by a co-investigator to obtain more information about the study. At the first point of contact (usually a phone call or Zoom Enterprise call), a

study co-investigator will administer an online-prescreening questionnaire. Once the online pre-screening process is complete, the information gathered by the co-investigator will be taken to the PI of the study for further review to confirm eligibility. Data obtained from the pre-screening will be stored in an encrypted web-based platform (REDCap).

When contacting subjects by email, we will communicate through the Massachusetts General Brigham network as per the institutional policy regarding secure email communication using encryption by Mass General Brigham / Partners Healthcare “Send Secure” function. If the first method of contact with the subject is through email, we will explain that they will receive encrypted emails going forward. This initial unencrypted email will have instructions on how to open encrypted emails. We will also explain that they can opt out of secure emails after informing them of the possible security risks. If they choose this option, this preference will be noted in our contact log.

The online informed consent will be obtained by the study PI and/or a co-investigator using the REDCap platform approved by Massachusetts General Brigham network (MGB REDCap eConsent). The PI will be available if the subject wants to discuss the trial with them or have any questions. The study procedures will be described, and the equipment will be shown to the subject. Study co-investigators will clearly explain all the procedures and risks of the testing outlined in the consent form. The subject will be given the time needed to consider their decision and will be encouraged to ask questions, both during the initial online interview (phone or Zoom Enterprise call) and throughout the study. The PI or a co-investigator will answer any questions regarding the study at the time consent is given. Once enrolled, the subject may pause or terminate his/her participation at any time during the study.

5. Subject Enrollment

We will enroll up to 60 subjects to find about 44 subjects, that will be randomized (by web-based program randomization.com) into 2 Groups (allocation ratio 1:1): active taVNS group (active taVNS) or sham taVNS group (sham taVNS). Randomization order will be placed into sequentially numbered sealed envelopes by an otherwise uninvolved staff member. Allocation concealment will be maintained throughout the study. Blinding will be maintained for participants and co-investigators not performing taVNS, including outcome assessors.

All study procedures will be done at the Spaulding Neuromodulation Center/Spaulding Cambridge Hospital.

In case of non-English speakers, a translated version of a ‘short form’ consent document will be used to document the informed consent when a non-English speaking individual is unexpectedly encountered and a written translation of the Mass General Brigham IRB-approved consent form is not available. In that case the consent process will follow these procedures:

- The subject will be given a written translation of the ‘short form’ consent document in the language understandable to them to read and must have the opportunity to ask and receive answers to questions.
- The entire consent process will be witnessed by an individual who is fluent in both English and the language understandable to the subject. The interpreter may serve as the witness, if they are willing to do so, to the consent process (presentation of the information in the consent form in

the language understandable to the subject and the opportunity to ask and receive answers to questions)

- The Mass General Brigham IRB-approved English version of the consent form will be signed by the investigator obtaining informed consent and the witness to the consent process.
- The written translation of the 'short form' must be signed by the subject and the witness to the consent process.
- The translator present for the consent process will be from the MGB Interpreter Services

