6. STUDY PROCEDURES

Study Outline

Pre-screening Procedures:

During the pre-screening process, the subject can contact a co-investigator, usually via encrypted Zoom Enterprise call, and REDCap form. During the pre-screening process, the co-investigator will discuss the details of the study, explain the study procedures, and encourage the subject to ask questions. In the privacy of the encrypted Zoom Enterprise call for healthcare, the co-investigator will ask the subject questions from the following:

- 1) Online Screening questionnaire
- 2) Phone Pre-screening questionnaire

Once this information is collected, the co-investigator will consult with the PI regarding the eligibility of the subject, who will then give the approval for the subject to come to our laboratory for the screening procedure.

Visit 1

Online or in-person Screening and Consent Visit – (Approximate Time: 1 hour)

If in-person, the visit 1 can be performed together with the visit 2 - (Approximate Time: 3 hours and 30 min).

If done remotely; the documentation would be signed electronically, and the visit would be done by telephone or using Zoom Healthcare)

During the Screening, the PI and/or a co-investigator will conduct once more a review of inclusion/exclusion criteria to determine the subject's eligibility for enrollment. If the consent is conducted by the co-investigator, the PI will review and sign off. Study procedures will be reviewed with the subject, and documentation of informed consent will be obtained. We will use an encrypted web-based platform (REDCap e-consent module) via Zoom call (Enterprise plan). Both services are already validated and in use by the MGB network.

- Discuss study-specific procedures with the subject.
- Review inclusion and exclusion criteria.
- Obtain a signed and dated consent form.
- Conduct a Demographics Survey, Brief Medical History, Beck depression inventory (BDI), and the Edinburg Handness Inventory Short form (EHI/SF).

Visit 2

Baseline Visit and First taVNS session – (Approximate Time: 2 hours and 30 min).

Urine pregnancy exam (if applicable).

Baseline assessments:

- EEG
- HRV
- QST
- The Brief Mood Introspection Scale (BMIS)
- Visual Analogue Scale to Evaluate Fatigue Severity (VAS-F) adaptation using tiredness item.

After the Baseline assessments:

Subjects will receive one session of either active taVNS or sham taVNS for 60 min. During the stimulation both groups will also be assessed with EEG, HRV, and VAS-F.

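### The emergency-room escort triggered by BDI question 9 cannot be carried out as written when Visit 1 is held by telephone or video

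*Combined protocol and SAP*

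**What the plan says.** The suicide-risk rule is in the note under the exclusion criteria in Section 4. It has two steps. For a subject who presents with suicidal ideation, "the medical monitor will be contacted to provide further evaluation and instruction". In addition, "Study participant will be escorted to the emergency room for assessment and triage" in the event of "spontaneous expression of suicidal ideation and/or BDI question 9 answers of 2 or 3". Neither step mentions whether the contact is on site or remote.

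The BDI is a Visit 1 procedure. Section 6 lists it there ("Conduct a Demographics Survey, Brief Medical History, Beck depression inventory (BDI"), and the visits schema at the end of Section 3 marks it in that column and no other.

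The mode of Visit 1 is described in different ways. The schema column is headed "Visit 1 (online". Section 6 calls the visit "Online or in-person Screening and Consent Visit". It adds that, in the remote form, "the visit would be done by telephone or using Zoom Healthcare", and that an in-person Visit 1 may be combined with Visit 2. By contrast, the last sentence of Section 5's site description places every study procedure at the hospital site, and the pre-screening text in Section 6 has approved subjects coming to the laboratory to be screened.

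**The concern.** An escort needs a staff member and the participant in the same place. The questionnaire item that triggers it is collected at a visit that the plan expressly allows by telephone or video, and that the schema shows only as online. A screener who receives an answer of 2 or 3 on a call would have to depart from the protocol or improvise.

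What is at stake is participant safety at screening, and whether staff have an instruction that they can follow at the moment they need it. The point has no bearing on the trial's analysis or inference.

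**Working it through.** No arithmetic applies, because the plan gives no figure on this point. The check sets the relevant passages side by side.

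1. **The action.** Section 4 requires an escort to the emergency room. It states no exception and cross-refers to no other procedure.

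2. **The triggers.** There are two. The first is a BDI question 9 answer of 2 or 3, which exists only where the BDI is completed. The second is spontaneous expression of suicidal ideation, which is tied to no visit and could occur at any contact, including on site at Visit 2. As worded, neither trigger depends on the total BDI score of more than 30 that defines exclusion criterion 7, so a person could meet the question 9 trigger without meeting that criterion.

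3. **Where question 9 is answered.** It is answered at Visit 1 only. Neither the schema nor the Visit 2 list in Section 6 repeats the BDI.

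4. **Mode by mode.**

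| Mode of Visit 1 | Permitted by | Medical-monitor contact possible? | Escort possible as written? |
|---|---|---|---|
| In person, alone or combined with Visit 2 | Section 6 | Yes | Yes |
| Telephone or video | Section 6; schema heading | Yes | No |

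5. **A remote substitute.** No readable text gives one. The medical history form described in Section 6 collects emergency and primary care contacts, but nothing links them to the suicide-risk rule. The medical monitor is to give further evaluation and instruction, but nothing says that this instruction stands in for the escort.

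6. **The on-site statements.** If the site sentence in Section 5 and the laboratory wording in the pre-screening text governed, Visit 1 would always be on site and the rule would work. They cannot be read that way without cancelling the explicit remote option in Section 6 and the schema heading. They are a further inconsistency to settle.

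7. **A parallel in the same table.** The schema also places the pregnancy test in the online column, whereas Section 6 puts the urine test at Visit 2, on site. For that item the procedures text gives a workable setting. For the BDI and its consequence it does not.

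**The case against.** The strongest reply is that this is missing operational detail and not a conflict. Section 4 names no setting, Section 6 permits an in-person visit, and in that mode the rule works. Part of this stands: the difficulty is confined to the remote mode. But remote screening is a planned mode, and a rule stated without exception cannot be followed in it. That goes beyond detail left to a manual.

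A reader might infer that the escort is the plan's only mandatory action for these answers, or that a remotely screened person with suicidal ideation has no provision at all. The documents do not support either reading. Contacting the medical monitor is worded just as firmly, on an ordinary reading covers both triggers, and can be done by telephone. What remains is that the two steps are stated separately and nothing says that one replaces the other.

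A second fair objection is that the text between the end of Section 9 and the references in Section 12 is unreadable in the public copy. A remote procedure may be there. That rules out any claim that the plan as a whole lacks one. It does not remove the mismatch between Section 4, Section 6 and the schema, since Section 4 points to no such procedure.

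Finally, these are healthy volunteers, and few may trigger the rule. That may be so, but the documents give no rate.

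**Conclusion.** The point holds in a limited form. When Visit 1 is remote, the escort required by Section 4 cannot be carried out as written, and no readable text says what takes its place. Contact with the medical monitor remains available in that setting.

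The size cannot be stated. The gap affects only people who are screened remotely and also meet a trigger, and the documents give neither the remote share nor the trigger rate. A reader might take the enrolment ceiling of 60 in Section 5 as the number affected. It is only an upper limit on how many could be screened remotely. A reader might also assume that both triggers belong to Visit 1. Only the question 9 trigger does, and suicidal ideation voiced on site can be handled as written.

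The conclusion assumes that the remote option in Section 6 is meant to be used, and that the unreadable text does not already provide a remote procedure.

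**What to change.** Reconcile four places: the suicide-risk note in Section 4, the site statement in Section 5, the pre-screening and Visit 1 text in Section 6, and the Visit 1 column of the visits schema. After the change, the action stated for these answers should be one that can be carried out in every mode in which the BDI may be completed, and the documents should agree on what those modes are. If a remote procedure already exists in text not readable here, a cross-reference from Section 4 would show it.

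What the action should be, and how it is delivered, is for the investigator and medical monitor to decide. The cost is protocol wording only. No change to the sample size or analysis is needed.
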